## **4. Sample Size Calculation**

This study encompasses multiple stages including retrospective model development and prospective clinical validation. Each stage has distinct objectives, leading to differences in the basis and methods of sample size estimation. This section elaborates on the basis, parameter sources, and methods for sample size calculation in each part, and clearly presents the key calculation formulas.

### **Retrospective Study Phase**

We adopt the LLaVA-Med model as the base model and employ the Low-Rank Adaptation (LoRA) parameter-efficient fine-tuning strategy, with the task scenario focusing on medical image-text bimodal report generation and disease diagnosis. Since LLaVA-Med has already completed pre-training on large-scale image-text alignment data and possesses strong cross-modal alignment capabilities, the fine-tuning objective of this study mainly focuses on medical domain knowledge adaptation and enhancement of task-specific generation capabilities. In this context, most of the model's visual encoder and language backbone are kept frozen, with only the cross-modal interaction module and LoRA low-rank parameters updated, thereby significantly reducing the required data scale.

Comprehensively considering factors such as model parameter scale, number of modalities, task complexity, domain transfer span, and freezing ratio, and substituting the original pre-training scale of LLaVA-Med into empirical formulas, the effective fine-tuning sample size required for this study is estimated to be approximately 10,000–20,000 pairs of high-quality image-text samples. This sample size not only ensures stable semantic alignment and knowledge transfer between medical imaging and clinical text in the model but also balances the efficiency and resource controllability of LoRA fine-tuning.

### **Prospective Study Phase**

The sample size for the prospective validation of this study is determined based on statistical power analysis. Assuming the model achieves an accuracy of approximately 85% in the disease diagnosis task, compared with an 80% accuracy rate of manual diagnosis, with an expected detectable performance difference of 5%, a significance level ( $\alpha$ ) set at 0.05, and a test power ( $\beta$ ) set at 0.2, approximately 500–600 cases per group are required according to the binomial distribution sample size calculation formula, with a total of 1000–2000 newly enrolled cases needed to meet statistical significance requirements.

Considering potential loss to follow-up or data disqualification during the prospective study, the final plan is to collect complete multimodal data (including imaging, reports, and laboratory results) from approximately 2000 patients for model validation and performance analysis. This sample size ensures the accurate evaluation of the model's stability, generalization ability, and consistency with expert diagnosis in real-world clinical scenarios at a 95% confidence level.

## **5. Data Management and Confidentiality**

All records related to the identities of subjects shall be kept confidential, and such information shall not be disclosed to the public except as permitted by applicable laws and/or regulations.

## **6. Informed Consent**

Written informed consent must be obtained from subjects before implementing any research procedures. Patients shall be informed of the specific details of the study, as detailed in the Informed Consent Form. The specific process for obtaining informed consent includes: on the

premise that patients fully understand the study design and research objectives, the informed consent form shall be signed by the patients themselves and/or their authorized family members.

## **7. Adverse Event Reporting**

### **(1) Definitions**

- Adverse Event (AE): Any unfavorable medical occurrence (e.g., patient anxiety resulting from AI misinterpretation).
- Serious Adverse Event (SAE): An event that results in prolonged hospitalization, is life-threatening, causes death, or requires medical intervention.

### **(2) Reporting Procedures**

- Investigators shall report AEs to the Principal Investigator (PI) within 24 hours → report to the IRB within 72 hours;
- SAEs shall be reported to the Hospital Medical Administration Office simultaneously.

### **(3) Handling Measures**

Immediately discontinue the use of AI for the affected patient, initiate clinical remedial measures, and withdraw the patient from the study if necessary. SAEs must be reported via the hospital's internal Non-punitive Adverse Event and Near-miss Reporting System.

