## **3. Research Design and Methods**

### **Prospective Validation of a Multimodal Imaging Large Model**

#### **(I) Study Design Type and Methodology**

This study is a single-center prospective observational study, aiming to conduct prospective validation and optimization of the established medical multimodal large model based on real-time collected clinical multimodal data (imaging, medical records, laboratory tests, reports, etc.). No additional interventions will be imposed on patients' diagnosis and treatment processes during the study; relevant data will only be collected synchronously during routine clinical examinations and diagnostic procedures, making it a non-interventional, minimal-risk prospective study.

During the study period, all newly diagnosed cases meeting the inclusion criteria will be consecutively enrolled. The research team will conduct prospective inference and performance validation of the multimodal medical large model based on imaging findings, EMR text, and laboratory test data, systematically evaluating the model's performance in tasks such as disease diagnosis, lesion localization, and report generation. Study results will be compared with clinicians' actual diagnostic conclusions and pathological gold standards to verify the model's generalization ability and clinical applicability in real-world scenarios.

The overall study protocol includes the following phases:

1. **Case recruitment and data collection:** Patients undergoing imaging examinations in the hospital will be consecutively recruited according to pre-defined inclusion criteria. Study data are derived from routine clinical workflows, covering imaging data, EMRs, laboratory results, and radiology reports. All data will undergo de-identification and quality control before being entered into the study database, with only the minimum necessary information retained.

2. **Model application and inference:** The research team will deploy the multimodal model in the hospital's secure computing environment. For each enrolled patient, the model will automatically generate disease predictions, lesion localization results, and diagnostic reports based on their imaging data and corresponding clinical text.

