3. **Clinical comparison and result documentation:** The model outputs will be subject to double-blind evaluation by radiologists and clinicians from relevant departments, compared with the final pathological or clinically confirmed results, and the accuracy, consistency, and interpretability of model predictions will be documented.

4. **Model iteration and continuous validation:** On the premise of ensuring ethical and privacy compliance, the research team will use newly collected data for continuous model fine-tuning and validation, analyzing its stability and robustness across different disease types, devices, and operational conditions.

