## **(III) Patient Inclusion, Exclusion, and Withdrawal Criteria**

### **Inclusion Criteria**

1. Adult patients aged  $\geq 18$  years;
2. Undergoing imaging examinations (CT, MRI, ultrasound, etc.) in the hospital during the study period;
3. Examination items corresponding to the disease types or systems focused on by the study (hepatobiliary and pancreatic system);
4. Possessing at least complete imaging data and radiology diagnostic reports, with relevant medical record information as supplementary modalities;
5. Patients or their legal representatives signing an informed consent form, agreeing to the use of their de-identified data for scientific research model validation;
6. Case data passing quality review, with good imaging quality and standardized text records.

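### The study is labelled non-interventional, yet its safety section presupposes AI use that can reach care, and no rule withholds model output until the clinical diagnosis is recorded

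*Protocol*

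**What the plan says.** Section 3 (I) of the protocol states that nothing is added to patients' diagnosis or treatment, "making it a non-interventional, minimal-risk prospective study", and that "relevant data will only be collected synchronously during routine clinical examinations and diagnostic procedures". Under the model application phase, "For each enrolled patient, the model will automatically generate disease predictions, lesion localization results, and diagnostic reports". Study results are then compared with clinicians' "actual diagnostic conclusions and pathological gold standards to verify the model". Under the clinical comparison phase, "The model outputs will be subject to double-blind evaluation by radiologists and clinicians from relevant departments".

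The Statistical Analysis Procedures in section 3 (IV) accept either the clinical final diagnosis or pathology as gold standard for AUC, sensitivity, specificity, accuracy and F1-score, all of which are primary indicators. No order of preference between the two is given. The Secondary Outcome Indicators include a reduction in physician review time.

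Section 7 (1) offers "patient anxiety resulting from AI misinterpretation" as the example of an adverse event. Section 7 (3) instructs staff to "Immediately discontinue the use of AI for the affected patient, initiate clinical remedial measures".

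**The concern.** A model whose output reaches neither the patient nor the care team cannot make a patient anxious, and there would be no use of it to stop. Section 7 therefore assumes a flow of information that the design section appears to exclude. A site that followed section 7 as written could reasonably believe that using output in care is allowed.

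Two things are at stake. First, the primary diagnostic metrics need a reference formed without the model. Where the clinical final diagnosis serves as reference and has absorbed a model error, that error counts as a correct answer. Second, the comparison with clinicians needs conclusions reached unaided. A clinician who revises a conclusion after seeing output is no longer an independent comparator. Unless the order of events was recorded, analysts cannot find out after enrolment who saw output first.

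**Working it through.** The plan gives no figure on this point, so the check sets the provisions side by side.

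1. **Declared design.** Section 3 (I) rules out added interventions, and Research Data Sources in section 3 (IV) says that data collection does not interfere with care.
2. **Provisions that presuppose contact with care.** Section 7 (1) and (3) do so, through their example of harm and the instruction to stop AI use for one patient. The review-time indicator is compatible with physicians working with the output, but it could equally be measured in an off-line reading, so it adds little.
3. **Timing of inference.** The statement on synchronous timing concerns data collection. The model application phase says that output is produced for every enrolled patient, but not when this happens relative to the diagnosis and not to whom output may be released.
4. **Blinding.** The double-blind wording in the clinical comparison phase, and again for ratings in the Statistical Analysis Procedures, describes how outputs are assessed. It does not say who is blinded to what, does not exclude treating clinicians from the evaluators, and sets no order against the final diagnosis.
5. **Entry requirement.** Eligibility calls for "Possessing at least complete imaging data and radiology diagnostic reports". This makes it likely that the radiology report precedes inference. The radiology report is not the clinical final diagnosis, however, and medical records are only a supplementary modality at entry, so inference need not wait for the completed work-up.
6. **Consequence for the reference.** Because either a clinical diagnosis or pathology may serve, some cases can rest on a clinical reference alone. In those cases an adopted model error raises apparent accuracy.
7. **Consequence for the comparator.** Clinicians' conclusions could change in any exposed case, including cases with a pathological reference. A clinician helped by a correct output would make manual diagnosis look better and narrow the model's advantage.

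Steps 6 and 7 can pull in opposite directions. To size the effect one would need the share of cases seen before diagnosis, the share that rest on a clinical reference, and how often clinicians change their view. The protocol gives none of these, so neither the size nor the net direction can be computed.

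**The case against.** The strongest reply is that the operating rule stands in section 3 and that section 7 is contingency text, perhaps from a template. A safety section may cover unintended disclosure without planning for it, and the anxiety case is only an example. The operational details also lean towards off-line use: de-identification before data enter the study database, a secure computing environment, a radiology report required at entry, and discharge summaries and surgical records among the text sources, which are normally written after the work-up.

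Much of this stands. A reader might infer from section 7 that output is in fact shown during care, or that the reference standard is contaminated. The documents do not support either reading; they show a contradiction and a missing safeguard. The reply does not remove the gap, because none of these details fixes the order of output and final diagnosis. If silent running is already intended, saying so costs almost nothing.

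Two reassuring readings also go too far. A reader might take pathology-referenced cases to be safe, but pathology protects only the reference, and the clinician comparator could still change in those cases. A reader might also think that locking the output makes model and reference independent. It does not: the discharge summaries and surgical records listed under Research Data Sources may hand the model the diagnosis as input, and withholding output does nothing about that.

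**Conclusion.** The point holds as an internal contradiction together with a missing rule. The protocol calls the study non-interventional, its safety section presupposes AI use that can touch the patient or care team, and nothing holds output back until the clinical final diagnosis and the clinicians' comparator conclusions are recorded. Exposure is possible but not established, and the size of any bias cannot be derived.

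The conclusion rests on two readings: that section 7 means what it says, and that the clinical final diagnosis serves as reference at least where pathology is absent, which is the natural reading but not a stated rule. The order of output and reference is a matter of design and conduct that belongs in the protocol. It should be settled before enrolment, since exposure that was not recorded cannot be reconstructed afterwards.

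**What to change.** - In section 3 (I), under model application and clinical comparison, state that output is withheld from treating clinicians and patients until the radiology report and the clinical final diagnosis are time-stamped and locked, and that evaluation of output starts only after the lock.
- Reword section 7 (1) and (3) so that they deal with inadvertent disclosure of output rather than with AI in use for a patient.
- Add a flag to the study database for any case in which output was seen before the lock.

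Sensitivity analyses, for example without flagged cases or in pathology-confirmed cases only, are optional and can be left to the SAP. Whether discharge summaries and surgical records may serve as model input needs separate attention, because the lock does not cover it.

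The cost is protocol wording, a time-stamp and a flag, with no extra patients or visits. The real downside is that physician review time cannot be measured in live care before the lock, so any such measurement has to come afterwards and is less close to practice.
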